**Prospective Evaluation of Foreign Body Airway Obstruction
Interventions Among Adults and Children: A Non-randomized
Pilot Cohort Study**

STUDY PROTOCOL AND STATISTICAL ANALYSIS PLAN

October 16th, 2025 – Version 1

October 27th, 2025 – Version 2

- Updated sample size calculation, and analysis of effectiveness outcomes.

Objectives

- Primary:
 - To determine the feasibility of prospectively identifying and recruiting patients with foreign body airway obstruction (FBAO) in Alberta, Canada.
- Secondary:
 - To determine the effectiveness and safety of basic life support (BLS) FBAO interventions among different patient age categories experiencing out-of-hospital FBAO

Research Question – Feasibility Study (Primary Objective)

1. What is the rate of eligible FBAO patients recruited per month through prospective identification in Alberta, Canada, and what proportion of satisfactory data collection is obtained?

Research Questions – Future Effectiveness and Safety Studies (Secondary Objective)

1. Among conscious adults and children with an out-of-hospital FBAO, which initial BLS FBAO intervention (abdominal thrusts, back blows or chest compressions) is more effective and safer?
2. Among conscious adults and children with an out-of-FBAO who failed initial management, is continuing the same intervention more effective than changing interventions?
3. Among conscious adults and children with an out-of-hospital FBAO who failed initial management, which BLS FBAO intervention or combination of interventions is more effective and safer?

Methods

Study Design

We will conduct a study to assess the feasibility of identifying and recruiting a prospective cohort of patients who experience an out-of-hospital FBAO in Alberta, Canada. The results of this pilot study will inform a future appropriately powered prospective cohort study examining the effectiveness and safety of FBAO interventions.

We will follow two reporting guidelines to ensure inclusion of all relevant sections:

- Consolidated Standards of Reporting Trials (CONSORT) extension to randomised pilot and feasibility trials [1]
- STROBE (Strengthening the Reporting of Observational Studies in Epidemiology) guideline [2]

The Conjoint Health Research Ethics Board of the University of Calgary (REB25-0419) and Alberta Health Services approved the study.

Setting

The study will be conducted in Alberta, Canada, where a single, publicly funded health authority (Alberta Health Services) delivers healthcare services, including emergency medical services (EMS) delivered by paramedics, to a population of 4.4 million people. Three levels of EMS care exist: Emergency Medical Responder (EMR), Primary Care Paramedic (PCP), and Advanced Care Paramedic (ACP). ACPS can perform advanced FBAO interventions like Magill forceps removal and intubation, while all levels receive training on basic interventions.

Study Population

Eligible patients will be adults or children aged older than 2 years who experience an out-of-hospital FBAO and are assessed by EMS or attend an emergency department for the incident. We define FBAO cases as individuals who present with a history of an object or substance not native to the airway introduced, followed by clinical signs of obstruction (e.g., stridor, cyanosis, hypoxemia, inability to move air) [3,4].

Only patients who are conscious when they receive the first FBAO intervention will be included. We will exclude cases where the patient has abnormal airway anatomy such as a tracheostomy, or who are unconscious upon receipt of first FBAO intervention.

Patient Identification

FBAO cases will be prospectively identified through two strategies:

1. A notification will be sent to researchers using Alberta Health Services' EMS electronic Patient Care Record (ePCR; Siren ePCR Version 4.6.26, Medusa Medical Technologies, Halifax, NS) when a case meets validated FBAO identification criteria based on paramedic diagnosis, protocol use, or treatment applied [4].
 - The ePCR is the sole paramedic prehospital charting system used in Alberta and therefore includes population-based data for the province, including demographics, vital signs, and standardized reporting of incident, patient, and treatment details. It also includes a free-text narrative synopsis, including information on the events preceding the FBAO, interventions performed by bystanders, patient assessments, and all interventions
2. A notification will be sent to researchers when a patient presents to an Alberta emergency department with an FBAO-related complaint (e.g., respiratory foreign body, respiratory arrest, stridor, dysphagia, cardiac arrest).

An emergency medicine physician will review identified cases to determine whether they meet the FBAO definition, based on the paramedic and emergency medicine

documentation, vital signs, and imaging. A second physician will review 10% of cases to ensure excellent interrater reliability (Cohen's kappa > 0.8).

Patient Recruitment and Consent

Adult patients, or the primary parent(s)/caregiver(s) of pediatric patients, will be contacted by a healthcare provider not affiliated with the research team once identified as an FBAO case to seek their interest in participating by telephone. If agreeable to participate, a research assistant will subsequently follow up with the patient (or parent/caregiver) to obtain informed consent and complete a short interview for data collection.

In the case that a patient is unable to participate in an interview due to severe injury, death, or inability to be contacted, then a waiver of consent has been obtained to use the medical record for data collection.

All eligible participants will be recruited consecutively. We will conduct the pilot over a period of 6 months from November 1st, 2025, to April 30th, 2026. If we proceed with a larger effectiveness study (see Sample Size below), the research team will decide based on available resources at that time if we will immediately continue with recruitment and include the pilot study's patients in the larger study's cohort.

Data Collection

Research assistants will conduct virtual structured interviews. We will develop a standardized data collection tool and pilot it among five individuals without healthcare or research training to ensure easy comprehension. Research assistants will receive training on the data collection tool before contacting patients.

In the situation where participants are unable to be interviewed, two research team members will extract data directly from the medical record independently and in duplicate. Disagreement between data extractors will be resolved by a third researcher. Data extractor agreement will be measured using Cohen's kappa.

Variables and Analysis by Research Objective

Primary Objective: Feasibility Study

Outcome: This study's primary focus is on the feasibility of prospectively identifying and recruiting FBAO patients, with the following outcome measures:

- Number of eligible patients recruited per month (Primary)
- Proportion of eligible patients recruited (Secondary)
- Proportion of recruited patients with $\geq 90\%$ of variables collected (Secondary)

Exposure: Given the primary aim of the feasibility study is a descriptive analysis of the outcome variables, no exposure variable is defined.

Sample Size: Abdominal thrusts and back blows are the two primary FBAO interventions used on adults and children, so the sample size is based on data of these two techniques

[3]. We estimate that 640 patients will need to be recruited to obtain 80% power using a statistical significance of 0.05 and two-sided z-test of independent proportions to detect, with successful proportion of abdominal thrusts and back blows equal to 59.5% and 72.2% respectively, with a ratio of patients who received abdominal thrusts versus back blows equal to 3.5 [3].

To complete an intervention effectiveness study in 48 months, we would need to recruit a mean of 13.3 patients per month. The slowest acceptable recruitment rate would be if recruitment required one additional year to obtain our desired sample size (60 months total). This would require recruitment of 10.6 patients per month. Using the traffic light approach for a feasibility study's sample size, we set the green criterion (progression, no concerns) to 13 patients or more per month and the red criterion (major problems, potentially not remediable concerns) to less than 10 patients per month. The amber zone will be set as 10-13 patients per month, which represents a recruitment rate range that may be compatible with a successful future study; however, we will first aim to identify and address remediable recruitment challenges before deciding whether to proceed [10].

Analysis: We will conduct a descriptive analysis of the recruited cohort's demographics, as well as the FBAO incident situational factors (categorical: frequency and proportions; continuous: medians and interquartile ranges). We will calculate the mean recruitment rate by dividing the number of recruited patients over the entire study period by the number of months recruitment was ongoing. We will track the number of patients who were eligible over the entire study period and determine our proportion of successful recruitment by dividing the count of recruited patients by the count of eligible patients. Finally, among our recruited patients, we will review the data collection forms and determine the number of patients who had 90% or more of variables obtained to ensure satisfactory data collection processes are in place.

Secondary Objectives: Effectiveness and Safety

Outcomes: The feasibility study will inform the development of several future studies investigating the secondary objectives focusing on FBAO intervention effectiveness and safety. These objectives' outcome variables will be:

- FBAO relief: defined as successful if the responder(s) determines that the patient did not require further FBAO intervention due to improvement/resolution of their respiratory distress (Primary)
- Survival to acute care discharge (e.g., Emergency Medical Services [EMS], emergency department, or hospital discharge). If transferred to a long-term care facility due to permanent neurological function decline, we will still consider this an acute care discharge (Secondary)
- Survival to discharge with favourable neurological outcome (Secondary): defined as the patient being able to be discharged to their previous home environment, with the ability to perform the same activities of daily living as before the FBAO incident
- Intervention-associated injuries (Secondary)

Question One: Among conscious adults and children with an out-of-hospital FBAO, which initial BLS FBAO intervention is more effective and safer?

- Exposure: Initial FBAO intervention (abdominal thrusts, back blows, chest compressions)

Question Two: Among conscious adults and children with an out-of-hospital FBAO who failed initial management, is continuing the same BLS intervention more effective than changing interventions?

- Population: Adults who experience an out-of-hospital FBAO and are attended by EMS or present to the emergency department in Alberta, Canada, and received at least 5 initial interventions (e.g., 5 abdominal thrusts)
 - For this question, we will require the patient received at least 5 unsuccessful initial interventions to capture only patients who do not respond immediately to initial treatment and require further intervention.
 - After 5 initial interventions, resuscitation guidelines recommend either continuing the initial intervention (Heart and Stroke Canada, and American Heart Association [5]) or alternating to another technique (European Resuscitation Council, Canadian Red Cross, and Lifesaving Society Canada [6-9]). By excluding the patients that initially responded to 5 or less attempts, we are creating a more similar patient population when comparing alternating techniques (e.g., abdominal thrusts and back blows) versus those who continued the same technique (e.g., 20 abdominal thrusts) to help address resuscitation time bias.
- Exposure: Receiving a single BLS FBAO intervention versus an intervention combination (abdominal thrusts [AT], back blows [BB], chest compressions [CC], AT and BB, AT and CC, BB and CC) after an initial 5 attempts

Question Three: Among conscious adults and children with an out-of-hospital FBAO who failed initial management, which BLS FBAO intervention or combination of interventions is more effective and safer?

- Exposure: FBAO intervention combination (abdominal thrusts [AT], back blows [BB], chest compressions [CC], AT and BB, AT and CC, BB and CC)

Analysis: As this pilot study will be underpowered to accurately estimate precision of the outcomes, we will limit reporting of these results to a descriptive analysis. We will include descriptive statistics of the patients' demographics and FBAO incident situational factors for the total study population, as well as stratified by the exposure variable (categorical: frequency and proportions; continuous: medians and interquartile ranges). We will also report descriptively the outcome variables listed above.

We will summarize missingness of all variables to determine appropriateness of imputation for future studies.

We will perform similar analyses for several subgroups: adults (aged ≥ 13 years), children (aged 3-12 years), patients residing in long-term care, patients with limited mobility, and patients who received first intervention with bystanders versus paramedics.

Covariates

Variable Name	Variable Type	Possible Values
Patient		
Age	Continuous	0 - 100
Sex	Categorical	Male, Female, Other
Estimated Patient Weight	Numerical	
Estimated Patient Height	Numerical	
History of Choking	Categorical	Yes, No, Unknown
Medical Comorbidities	Open response	Free Text
Specifically ask: Stroke, Dementia or Alzheimer's, Difficulty Swallowing or Chewing, Parkinson's Disease	List, select all that apply	Any of the specific answers
Pre-FBAO ADL Independence	Categorical	Independent, Dependent, Unknown
If Dependent: Which ADLs require assistance? Which ADLs are completely dependent?	List, select all that apply	Ambulation/mobility, Eating/feeding, Personal hygiene/bathing, Dressing, Toileting
If Limited Mobility: What is their mobility?	Categorical	Walk independent, Uses cane, Uses walker, Uses wheelchair, Limited to bed
Long term care resident	Categorical	Yes, No, Unknown
Situation		
Location	Categorical	Home, Long term care residence, Restaurant, School, Other public place, Unknown
Foreign body	Open response	Free text
Witnessed Status	Categorical	Witnessed, Unwitnessed, Unknown
Witness Relation	Categorical	Family or friend (known person), bystander (unknown person), Unknown
Bystander Response		

Dispatcher Instruction	Categorical	Given, Not Given, Unknown
Bystander Response	Categorical	Yes, No, Unknown
If Bystander Responded:		
Bystander Sex or Gender	Categorical	Male, Female, Other, Unknown
Bystander (estimated) Age	Continuous	0 - 100
Bystander (estimated) Weight	Continuous	
Bystander (estimated) Height	Continuous	
Bystander Training	Categorical	Healthcare training, First aid/CPR/BLS, None, Unknown
Patient Status During Bystander Response	Categorical	Conscious/responsive + talking/crying/effective cough; Conscious/responsive + ineffective cough/no sounds; altered; unresponsive/unconscious
Initial Bystander Intervention	Categorical	Abdominal Thrusts, Back Blows, Chest Compression, Suction Devices, Other, Unknown
Number of Initial Intervention Attempts	Numeric	0 - 100
Initial Intervention Success	Categorical	Yes, No, Unknown
How Was Success Determined	Open response	Free text
Repeat for Each Bystander Intervention		
EMS and Emergency Department Response		
EMS Called	Categorical	Yes, No, Unknown
If EMS Attended		
Patient Still Choking when EMS Arrives	Categorical	Yes, No, Unknown
Patient Status During Paramedic Response	Categorical	Conscious/responsive + talking/crying/effective cough; Conscious/responsive + ineffective cough/no sounds; altered; unresponsive/unconscious

Initial Paramedic Intervention	Categorical	Abdominal Thrusts, Back Blows, Chest Compression, Suction Devices, Other, Unknown
Number of Initial Intervention Attempts	Numeric	0 - 100
Initial Intervention Success	Categorical	Yes, No, Unknown
How Was Success Determined	Open response	Free text
Repeat for Each Paramedic Intervention		
Intubated on scene	Categorical	Yes, No, Unknown
Cardiac arrest on scene	Categorical	Yes, No, Unknown
Transported to hospital	Categorical	Yes, No, Unknown
Management in the Emergency Department	Open Response	Free text
Other Outcomes		
Survived to acute care discharge	Categorical	Yes, No, Unknown
Post-FBAO ADL Independence	Categorical	Independent, Dependent, Unknown

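### Entry needs EMS or emergency department contact, which for bystander-treated patients can follow and depend on relief; relief by initial technique may be distorted, and Question One is worded more widely than the cohort

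*Combined protocol and SAP*

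**What the plan says.** - **Entry** (Study Population): patients qualify if they are those "who experience an out-of-hospital FBAO and are assessed by EMS or attend an emergency department for the incident".
- **Identification** (Patient Identification): on the EMS route, the electronic patient care record (ePCR) flags a case "based on paramedic diagnosis, protocol use, or treatment applied". The second route is a notification when a patient presents to an emergency department with a related complaint.
- **Outcome** (Secondary Objectives, Outcomes): relief is the primary effectiveness outcome, "defined as successful if the responder(s) determines that the patient did not require further FBAO intervention".
- **Bystanders are in scope** (Analysis of the secondary objectives; Covariates): one planned subgroup is "patients who received first intervention with bystanders versus paramedics". The form records each bystander intervention and its success.
- **Relief before contact is foreseen** (Covariates): the form has an item "Patient Still Choking when EMS Arrives". The item on whether EMS was called is Yes, No or Unknown, with no timing.
- **Target population**: Question One reads "Among conscious adults and children with an out-of-hospital FBAO, which initial BLS FBAO intervention is more effective and safer", with no restriction to attenders. Question Two's population line is restricted: "Adults who experience an out-of-hospital FBAO and are attended by EMS or present to the emergency department in Alberta, Canada".
- **Bias named**: the plan restricts Question Two to patients with at least five unsuccessful attempts "to help address resuscitation time bias". Selection on relief is not mentioned for any question.

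**The concern.** In a cohort study of first treatment, entry should not depend on the outcome. Here it can. When a bystander acts first, the responder may already have judged relief when someone decides whether to call EMS or go to an emergency department. A patient relieved at once may never make contact, while one still obstructed has a strong reason to.

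Three consequences need separating:

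1. If relieved patients enter less often than unrelieved ones, relief among bystander-first patients reads too low.
2. If that relative chance of entry differs between techniques, a difference can appear where none exists. The same can happen in the whole cohort if one technique is used more often by bystanders.
3. If entry depends on relief to the same degree for both techniques and the responder mix is the same, equality and the odds ratio are preserved. The proportions and their difference still change.

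A larger sample removes none of these. The pilot is meant to inform the powered study, and its patients may be carried into that cohort. If the timing of contact is not asked at interview now, it may be hard to recover later.

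**Working it through.** **The plan's own figure.** Sample Size gives 59.5% relief with abdominal thrusts, 72.2% with back blows, a 3.5:1 ratio, two-sided 0.05 and 80% power. With pooled variance and no continuity correction:

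- weighted mean proportion = (0.722 + 3.5 × 0.595)/4.5 = 0.6232
- back-blow group = [1.960 × √(0.6232 × 0.3768 × (1 + 1/3.5)) + 0.842 × √(0.722 × 0.278 + 0.595 × 0.405/3.5)]² / 0.127² = 142.1
- total = 142.1 × 4.5 = 639.4, so 640 (644 if each group is rounded up)

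The 640 reproduces. The planned difference is 12.7 points and the odds ratio is (0.722/0.278)/(0.595/0.405) = 1.77.

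**Inputs not in the documents (assumptions).** True relief r; share a of relieved bystander-first patients who enter; share w of a technique's patients who are bystander-first. All unrelieved and all paramedic-first patients are taken to enter, with the same r for both kinds of responder.

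Observed relief = r(wa + 1 − w) / [r(wa + 1 − w) + 1 − r]. With w = 1 this is ra/(ra + 1 − r).

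**No true difference, r = 0.7, entry of relieved patients differs by technique**

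| Bystander-first share w | a = 0.5 v 0.3 | Gap | a = 0.4 v 0.3 | Gap |
|---|---|---|---|---|
| 1.00 | 53.8% v 41.2% | 12.7 points | 48.3% v 41.2% | 7.1 points |
| 0.75 | 59.3% v 52.6% | 6.8 points | 56.2% v 52.6% | 3.6 points |
| 0.50 | 63.6% v 60.3% | 3.4 points | 62.0% v 60.3% | 1.8 points |

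Worked entries: for w = 1, 0.35/(0.35 + 0.30) = 0.538 and 0.21/(0.21 + 0.30) = 0.412. For w = 0.5, 0.525/(0.525 + 0.30) = 0.636 and 0.455/(0.455 + 0.30) = 0.603.

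**No true difference, r = 0.7, a = 0.5 for both techniques, only the responder mix differs.** With w = 0.9 for one technique and 0.6 for the other, observed relief is 0.385/0.685 = 56.2% and 0.49/0.79 = 62.0%, a 5.8-point gap. Within the bystander-first group alone there is no gap, so the planned subgroup deals with this route. It does not deal with the route in the table above.

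**Same relative entry for both techniques, w = 1.** If the true proportions were the planned ones:

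| a | Abdominal thrusts | Back blows | Difference | Odds ratio |
|---|---|---|---|---|
| 1 | 59.5% | 72.2% | 12.7 points | 1.77 |
| 0.75 | 52.4% | 66.1% | 13.7 points | 1.77 |
| 0.5 | 42.3% | 56.5% | 14.1 points | 1.77 |
| 0.25 | 26.9% | 39.4% | 12.5 points | 1.77 |

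**Relaxing full entry of failures (w = 1, r = 0.7).** If 70% of first-technique failures enter, a = 0.4 v 0.3 gives 0.28/(0.28 + 0.21) = 57.1% and 0.21/(0.21 + 0.21) = 50.0%. The gap is again 7.1 points, but the levels lie closer to 70%.

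**The case against.** **This is a pilot.** Recruitment and data completeness are the primary and secondary feasibility outcomes, and effectiveness results are limited to description. That stands: nothing inferential in the pilot is harmed. It does not dispose of the point, because the pilot informs the larger study and its patients may be pooled.

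**Failures need not all enter.** Question One concerns the first technique, and the form repeats success for each later one. A patient whose first technique failed may be relieved by a second and never attend. This stands. A reader might infer that relief is understated for every bystander technique, but the documents do not establish that; it holds only if relieved patients enter less often than unrelieved ones.

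**The artefact need not rival the planned effect.** A reader might set the 13-point illustration beside the planned 12.7 points and conclude that selection alone could produce it. That illustration is for an all-bystander cohort, whereas the planned cohort includes paramedic-first patients. Nothing in the documents shows that attendance differs by technique.

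**Existing items help.** The item on whether the patient is still choking at EMS arrival, the dispatcher-instruction item and the ePCR narrative give partial information. But the first shows whether relief came before arrival, not whether the call came before relief, and splitting on it conditions on the outcome. The absence of dispatcher instructions does not time a call.

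**Early callers are not immune.** A reader might infer that patients whose call preceded the first intervention are free of this selection. They are not: a caller's patient relieved before the crew arrives may need no paramedic treatment or protocol, and so may not be flagged.

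**Conclusion.** The point holds in conditional form. Entry can follow and depend on relief for bystander-treated patients, the form does not time the contact, no section addresses the selection, and Question One is wider than the eligible population. Size and direction are unknown. In the illustrations with no true difference, the gap runs from zero (equal entry, equal responder mix) through about 3 points (half bystander-first, 50% v 30%) to 13 points (all bystander-first, 50% v 30%). All rest on assumed attendance shares, 70% true relief and full entry of unrelieved and paramedic-first patients.

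A reader might go further and take the pilot's primary result to be compromised. The documents do not support that: recruitment per month, proportion recruited and data completeness are defined on eligible or recruited patients. What is affected is the descriptive relief table, the inputs it supplies to the larger study, and any pooled cohort. This is a cheap improvement worth making, not a flaw that stops the pilot.

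**What to change.** 1. **Form.** Replace the Yes/No/Unknown item on calling EMS with: called before first intervention; after first intervention began but before relief; after relief; not called; unknown. For patients who reached an emergency department without EMS, record whether the decision to attend came before or after relief.
2. **Table.** Keep the overall Question One table. Beside it, report relief by technique for patients whose call preceded the first intervention (including paramedic-first patients) and for all others. Describe the first group as less exposed to this selection, not free of it, because flagging depends on paramedic diagnosis, protocol or treatment.
3. **Wording.** State Questions One and Three, and their conclusions, for FBAO assessed by EMS or in an emergency department, in line with Question Two's population line.

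The cost is form items that rest on recall of an emergency, one supplementary table and a wording change. Cells will be small: 10 to 13 patients a month over 6 months is 60 to 78 patients, and at 3.5:1 about 13 to 17 of them have back blows (60/4.5 and 78/4.5) before any split. That is why the split should supplement the overall table and not replace it. Eligibility and recruitment targets do not change.

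### Death and severe injury lead to cohort entry by waiver while contacted patients can decline, so crude survival and favourable neurological outcome are understated if refusals occur

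*Combined protocol and SAP*

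**What the plan says.** Patient Recruitment and Consent sets up two routes into the cohort.

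- **Consent route.** A healthcare provider outside the research team telephones the patient, or a child's parent or caregiver. "If agreeable to participate, a research assistant will subsequently follow up with the patient (or parent/caregiver) to obtain informed consent" and carry out the interview.
- **Waiver route.** For anyone "unable to participate in an interview due to severe injury, death, or inability to be contacted, then a waiver of consent has been obtained"; their data come from the chart. Data Collection adds: "In the situation where participants are unable to be interviewed, two research team members will extract data directly from the medical record".

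The same section states: "All eligible participants will be recruited consecutively". Nothing says what happens to a patient or caregiver who is reached and declines. By implication they are left out, because the waiver does not name them.

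The feasibility analysis states: "We will track the number of patients who were eligible over the entire study period". It will also "determine our proportion of successful recruitment by dividing the count of recruited patients by the count of eligible patients". The analysis paragraph after Question Three limits the effectiveness and safety results to description: "We will also report descriptively the outcome variables listed above". Those outcomes are relief, survival to acute care discharge, survival with favourable neurological outcome, and intervention-associated injuries. No split by entry route is planned. The planned missingness summary concerns variables, not eligible patients who never entered.

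**The concern.** Two of the three waiver triggers, death and severe injury, coincide or overlap with the outcomes being reported. A patient who dies is in the cohort with certainty. A survivor who is reached is in only if someone agrees. Entry therefore depends on outcome, and the proportions among those who entered need not match those among the eligible.

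Consecutive recruitment does not repair this, because it governs who is approached and not who agrees. The eligible count that would expose the problem is tracked, but used only for the recruitment proportion.

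What is at stake is the descriptive survival and neurological figures that readers will take from the pilot. The distortion would also pass into the larger study if the pilot's patients are carried into that cohort, which the protocol leaves open, or if the same entry rule is reused.

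**Working it through.** **The plan's own figures.** The documents give no refusal rate, no uncontactable share and no survival rate, so there is no stated figure on this point to reproduce. The only related inputs are the relief proportions in the sample size paragraph (59.5% for abdominal thrusts, 72.2% for back blows, ratio 3.5). These reproduce the planned 640: a pooled two-sided z-test at 0.05 and 80% power gives 143 + 501 = 644, and power at 640 is 80.04%.

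All inputs below marked as assumed are illustrations.

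**Mortality.** Per 100 eligible patients, assume 5 deaths, 10 further waiver entries who survive (severely injured or not reachable) and 85 reached. With consent proportion c among those reached:

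reported mortality = 5 / (5 + 10 + 85c)

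| c | Patients in cohort | Reported mortality |
|---|---|---|
| 1.0 | 100 | 5.0% |
| 0.9 | 91.5 | 5.5% |
| 0.7 | 74.5 | 6.7% |
| 0.5 | 57.5 | 8.7% |

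**Survival over a wider range.** Let S be true survival, u the share of survivors who cannot be reached (they enter by waiver) and d the refusal proportion among survivors who are reached. A survivor enters with probability f = u + (1 − u)(1 − d), and a death with probability 1.

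reported survival = S·f / (S·f + 1 − S)

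With S = 90% (assumed):

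| u | d = 10% | d = 20% | d = 30% | d = 50% |
|---|---|---|---|---|
| 0 | 89.0% | 87.8% | 86.3% | 81.8% |
| 20% | 89.2% | 88.3% | 87.2% | 84.4% |

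Unreachable survivors dilute the bias without removing it. With d = 0 there is none.

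**Favourable neurological outcome.** Use the same 100 patients and assume that everyone reached has a favourable outcome. The answer depends on who the 10 other waiver entries are.

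- All 10 unfavourable: the truth is 85%. Reported is 85c / (15 + 85c) = 83.6%, 79.9%, 73.9% at c = 0.9, 0.7, 0.5.
- All 10 well but unreachable: the truth is 95%. Reported is (10 + 85c) / (15 + 85c) = 94.5%, 93.3%, 91.3%.

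Both extremes err downwards.

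**Relief.** Relief is not a waiver trigger. It matters only so far as failure of relief leads to death or severe injury. Assume that 2% of relieved and 25% of unrelieved patients enter by waiver for that reason, with u = 0. Entry probabilities are then 0.02 + 0.98(1 − d) and 0.25 + 0.75(1 − d).

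| | d = 10% | d = 30% | d = 50% |
|---|---|---|---|
| 59.5% becomes | 58.9% | 57.2% | 54.5% |
| 72.2% becomes | 71.7% | 70.3% | 67.9% |
| Difference (true 12.7 points) | 12.8 | 13.1 | 13.4 |

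Across three assumed pairs of waiver shares (1% and 10%, 2% and 25%, 5% and 40%), with equal refusal in both groups, the difference stays between 12.7 and 13.7 points.

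**Check of the remedy.** At c = 0.7 the eligible count is 59.5 consented + 15 by waiver + 25.5 declined = 100. Counting the decliners as alive gives mortality 5/100 = 5.0%, the true value, provided that all of them survive to discharge.

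**The case against.** The strongest reply is that the consequence is small. The plan calls the pilot underpowered and restricts these results to description. Progression depends only on recruits per month, and the future sample size uses relief proportions from a cited earlier cohort. At 10 to 13 recruits per month for 6 months, the cohort has about 60 to 78 patients. With 5% mortality that is 3 or 4 deaths, and the exact 95% intervals are about 1.0% to 13.9% (3/60) and 1.4% to 12.6% (4/78). Shifts of 0.5 and 1.7 points at 90% and 70% consent are minor beside that. All of this stands, and it limits the weight of the point. It does not remove it: the shift has a predictable direction, and unlike sampling error it would not shrink in a larger cohort under the same entry rule.

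Several stronger readings are tempting, and the documents do not support them.

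- *Every well survivor enters only by agreeing.* The waiver also covers people who cannot be contacted, so well survivors who are never reached do enter.
- *Everyone lost is alive and without severe injury.* For children the parent or caregiver is approached, and the parent of a severely injured child might be reachable and decline. The text does not settle this case.
- *Injuries are overstated.* The waiver concerns injury that prevents an interview, whereas the outcome is intervention-associated injury of any grade, recorded as free text. Minor injuries may be under-recorded in chart-only patients, which pulls the other way.
- *The comparison of techniques is compromised.* With similar refusal across techniques it hardly moves.

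It can also be objected that decliners should not be assigned an outcome. That is fair, so the all-eligible figure belongs beside the crude one with its assumption stated.

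**Conclusion.** The point holds conditionally. If contacted patients or caregivers decline, those lost are almost all survivors. Crude survival and favourable neurological outcome are then understated, and injuries severe enough to prevent an interview are over-represented. Nothing in the planned analysis would reveal or correct this.

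The size cannot be fixed from the documents. On assumed inputs of 5% mortality and 10% other waiver entries, reported mortality is 5.5% to 8.7% as consent falls from 90% to 50%. The direction rests on decliners having better outcomes than the patients who enter because of death or severe injury, which follows from the entry rule apart from the caregiver case. A reader might infer that the bias is certain, or that it reaches the go/no-go decision. Neither follows: it is nil without refusals, and the progression criteria use no clinical outcome. This is a cheap improvement to secondary, descriptive results.

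**What to change.** In the analysis paragraph of Secondary Objectives: Effectiveness and Safety, add:

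1. Survival to acute care discharge is reported twice: among patients in the cohort (crude), and over all eligible patients, with contacted decliners counted as alive at contact. The second figure is labelled as assuming that they survive to discharge.
2. Counts are given of patients who consented, entered by waiver (separately for death, severe injury and no contact) and declined. All clinical outcomes are shown by entry route.

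Patient Recruitment and Consent should also state how refusals are handled, whether they occur at the first telephone call or at the research assistant's follow-up.

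Weighting consenters by the inverse of the consent proportion among those reached, with waiver patients at weight 1, is optional as a sensitivity analysis. It assumes that decliners resemble consenters, and it is hard to justify as a requirement in about 60 to 78 patients.

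Cost: a refusal log, SAP wording and one extra table. The eligible count is already tracked, and no record data from decliners are needed. The remaining weakness is that a decliner who dies after contact would be misclassified as a survivor.
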